SADE	Serious Adverse Device Event
SDAI	Simple Disease Activity Index
7T	Tesla
TMG	Trial Management Group
TMS	Transcranial magnetic stimulation

STUDY SYNOPSIS

Title of Study	Probing the Rheumatoid Arthritis Brain to Elucidate Central Pain Pathways
Study Centre	University of Glasgow/NHS Greater Glasgow and Clyde
Duration of Study	24 months
Primary Objective	To evaluate changes in neural glutamate, neuronal signal cohesion and functional connectivity in RA patients following L-IPL stimulation using TMS
Secondary Objective	To evaluate changes in pain severity and characterisation, RA disease activity, sickness behaviour and peripheral inflammatory markers in RA patients following L-IPL stimulation using TMS
Primary Endpoints	The primary endpoints are - Changes in functional connectivity and neuronal signal cohesion after TMS/sham therapy, as measured by 7T MRI - Changes in glutamate signal in the L-IPL after TMS/sham therapy, as measured by 7T MRS
Rationale	Many patients with rheumatoid joint disease continue to experience significant pain despite receiving apparently optimal joint specific therapies. We believe this discrepancy relates to the existence of pain sources which are supplementary to those present in the joints. In particular, we have been among the first to report evidence implicating the brain in the generation of this disabling problem. Brain scanning methods have helped us to identify a specific region (the left inferior parietal lobule (L-IPL)) which appears to be an important link between the characteristic excessive inflammation of RA and pain processing. We hope to better examine this possible link by employing a safe, non-invasive technique called transcranial magnetic stimulation (TMS). TMS uses a magnet to influence the function of a specific region on the brain surface. We will use TMS to target the left inferior parietal lobule and then assess participants for changes in aspects of brain biology (which have been considered important in other chronic pain disorders), their pain and markers of inflammation. Due to the inherent dangers of sampling the brain, we will instead use 7T magnetic resonance imaging to make indirect measurements of brain biology, including changes in specific chemistry. This information will help us to better understand the precise role of the left inferior parietal lobule in relation to pain. The results of this modest project will inform bigger, more definitive studies and will ultimately deliver knowledge that will allow us to address the tremendous shortfall of safe and effective pain relief strategies for patients with RA and beyond.
Methodology	This randomised, sham-controlled, crossover study will allow us to test the hypothesis that systemic inflammation results in haphazard neuronal signalling and heightened centralised pain using a single session of non-invasive TMS. In order to ensure that any observed changes are specific to TMS, subjects will be randomised equally to receive an initial single session of either active or sham procedure. The latter will employ the same equipment but will not generate a magnetic effect. Subjects will be asked to return 3 weeks later to receive the alternative procedure.
Sample Size	20 participants

Screening	Patients with active RA attending clinics in NHS Greater Glasgow and Clyde will be approached to contribute to this study by the point of care team.
Inclusion Criteria	
 • Adults \geq 18 years $<$ 75 years. • Physician diagnosis of RA • ACR definition of chronic widespread pain • Able and willing to maintain medication for the 6-week study duration • CRP $>$ 6mg/L or ESR $>$ 20mm/hr • \geq1 swollen joint • Right-handed (to reduce neuroimaging heterogeneity).
Exclusion Criteria	
 • Inability to provide written informed consent. • Severe physical impairment (e.g. blindness, deafness, paraplegia). • Pregnant, planning pregnancy or breast feeding. • Severe claustrophobia precluding MRI. • Contraindications to MRI (e.g. metal implants/ pacemaker). • Contraindications to TMS (e.g. history of seizures). • Serious infection including sepsis, tuberculosis and opportunistic infections such as invasive fungal infections. • Major confounding neurological disease including Multiple Sclerosis, Stroke, Traumatic Brain Injury, Parkinson's Disease, Alzheimer's Disease
Product, Dose, Modes of Administration	A single session of transcranial magnetic stimulation (TMS) of the left inferior parietal lobule (L-IPL) will be delivered using a figure of 8 coil at 10Hz, 90% resting motor threshold intensity and 1200 pulses. The TMS pulses will be given in series of 20 trains of 6s duration (with 54s intertrain intervals).
Duration of Study Participation	6-8 weeks
Statistical Analysis	
1) Descriptive statistics and data visualization. Median values and interquartile ranges of primary and secondary outcomes will be generated for each of the four time points. Paired plots for raw data and boxplots will be generated showing difference scores in the outcomes following sham and active TMS.
 
2) Hypothesis testing. Paired-difference tests for parametric data (paired sample t-tests) will be used to test our hypotheses by comparing the change in outcomes following sham TMS to the change in outcomes following active TMS. Hypothesis testing will be two-sided with alpha = .05, and 95% confidence intervals around the contrast will be generated using bootstrapping with 20,000 resamples.
 
3) Effect Size: As a simple expression of effect size, the proportion of subjects showing greater, equal and lesser reduction in glutamate between active and sham conditions will be reported. For the calculation of sample size estimates for future studies, the standardized mean difference effect size for within-subject designs (d-z) will be calculated.
 
4) Outcome inter-relationships: Exploratory correlations will examine the relationships between the different outcomes and their change

1 STUDY FLOW CHART

2 SCHEDULE OF ASSESSMENTS

Study Procedure	Screening Visit 1	Screening visit 2 [†]	Visit 1 (+/- 7 days)	Visit 2 (+/- 7 days)	Visit 3 (+/- 7 days)	Visit 4 (+/- 7 days)
Informed consent	✓					
Inclusion/exclusion criteria	✓					
Neuronavigation Scan		✓				
Motor Threshold Assessment		✓				
7T structural scans	✓					
Randomisation	✓					
Demographics	✓					
BMI	✓					
Family Medical History	✓					
Completion of Symptom Diary ^{††§}		✓	✓	✓	✓	
7T magnetic resonance protocol			✓*		✓*	
Pain, fatigue, and depression severity			✓*	✓	✓*	✓
Measure of disease activity	✓		✓	✓	✓	✓
Sickness Questionnaire			✓*	✓	✓*	✓
Pain confounder questionnaires [§]			✓	✓	✓	✓
Michigan Body Map Regional Pain [§]			✓	✓	✓	✓
Blood sample for immunophenotyping ^{†††}			✓*	✓	✓*	✓
TMS or sham procedure			✓		✓	
Recording of Adverse Events			✓	✓	✓	✓

[†] Screening visit will be conducted at the Centre for Cognitive Neuroimaging, University of Glasgow

^{††} Symptom diary will be completed for the 7 days following each visit

^{†††} Blood sample schedule outlined in 6.4 LABORATORY TESTS

^{*} Procedure will be performed twice; before **and** after TMS/Sham therapy

[§] Option to complete questionnaires remotely to reduce visit length

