6.1.1 Screening visit 1 (Day 0)

This screening visit will be conducted at the Queen Elizabeth University Hospital.

- Informed consent
- Review of inclusion / exclusion criteria
- Disease activity (SDAI / CDAI)
- 7T structural scans
- Randomisation
- Demographics
- BMI
- Medical History

Estimated visit time 1 hour

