6.1.2 Screening visit 2 (Day 7) (+/- 7 days)

This screening visit will be conducted at the Centre for Cognitive Neuroimaging, University of Glasgow.

- Neuronavigation scan
- Motor threshold assessment
- Completion of symptom diary (to be done at home, Days 8-14)

Estimated visit time 1 hour

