6.1.3 Visit 1 (Day 14) (+/- 7 days)

Visit 1 will be conducted at the Queen Elizabeth University Hospital

- 7T Neuroimaging protocol*
- Michigan Body Map Regional Pain[§]
- NRS for pain, fatigue, and depression*
- McGill Pain Questionnaire[§]
- Disease activity (SDAI / CDAI)
- Sickness Questionnaire*
- Pain confounder questionnaires[§]:
 - PROMIS-Fatigue (16-items)[§]
 - PROMIS-Depression (8 items)[§]
 - PROMIS-Anxiety (8 items)[§]
 - PROMIS-Sleep Related Impairment (8 items)[§]
 - PROMIS-Physical Functioning Short Form (8-items)[§]
 - PROMIS-Pain Interference (8-item)[§]

- ACR Fibromyalgia Scale[§]
- Venous blood sample for peripheral immunophenotyping*
- TMS or sham procedure
- Completion of symptom diary (to be done at home, Days 15-21)

**will be conducted before and after TMS/sham procedure*

§has the option to be completed remotely to reduce visit time

Estimated visit time 4 hours

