7.1.2 Motor Threshold Assessment

Screening visit 2 will also include assessment of the resting motor threshold. This will be used to standardise the intensity of active TMS used in a subsequent session. As is normal practice, single pulse TMS will be used to stimulate the left motor cortex, which will be located with the aid of neuronavigation. The motor threshold is the minimum intensity required to elicit a motor evoked potential in the contralateral hand in at least 50% of trials. This threshold is affected by individual differences in anatomy and cortical excitability, and therefore varies between participants.

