8.2 ADVERSE EVENTS (AEs)

An adverse event is any untoward medical occurrence, unintended disease or injury, or untoward clinical signs (including abnormal laboratory findings) in subjects, users or other persons, whether or not related to the investigational medical device.

Note 1 to entry: This definition includes events related to the investigational medical device or the comparator.

Note 2 to entry: This definition includes events related to the procedures involved.

Note 3 to entry: For users or other persons, this definition is restricted to events related to the use of investigational medical devices.

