8.5 RECORDING AND REPORTING OF ADVERSE EVENTS

Reports of non-serious Adverse Events (AE), Serious Adverse Events (SAE), serious adverse device events (SADE) or other errors outside of what is foreseen in the protocol (irrespective if a clinical event has occurred) will be reported to the CI and will be submitted to the Research Ethics Committee (REC) using the Non-CTIMP safety report to REC form.

Only reports of SAEs, non-serious AEs or SADEs that are 1. related to the study (i.e. they resulted from administration of any of the research procedures) and 2. unexpected (USADE) should be submitted.

These should be sent within 15 days of the CI becoming aware of the event. There is no requirement for annual safety reports in addition to the information provided through the annual progress report.

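### Scheduled adverse-event recording starts at Visit 1, after the screening 7T scan and the first real TMS pulses, although section 8 covers events from every research procedure

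*Protocol*

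**What the plan says.** The section 2 schedule has a row headed "Recording of Adverse Events". It is ticked at Visits 1, 2, 3 and 4, and the cells for Screening visits 1 and 2 are empty.

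Section 6.1.1 places consent, randomisation and the 7T structural scans at Screening visit 1 (Day 0). Section 6.1.2 lists "Motor threshold assessment" at Screening visit 2 (Day 7). Section 7.1.2 explains that for this assessment "single pulse TMS will be used to stimulate the left motor cortex". Visit 1, the first visit with an adverse-event tick, is nominally on Day 14 (6.1.3).

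Section 8 is wider than the schedule. Under the definition of an adverse event, 8.2 notes: "This definition includes events related to the procedures involved". Section 8.5 describes study-related events as those where "they resulted from administration of any of the research procedures". Neither section says when recording begins. Section 5.7 asks for the details of any withdrawal to be entered on the eCRF, and section 9.2 plans a descriptive summary of serious adverse events only.

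**The concern.** The schedule of assessments is what site staff follow at each visit. Followed as it stands, it prompts nobody to ask about adverse events at either screening visit, although section 8 treats events from the procedures done there as adverse events of the study. The two parts of the protocol disagree about when safety recording starts.

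What is at stake is the completeness of the safety record. The study describes itself as a feasibility study piloting a TMS protocol to inform a larger one (3.2), and thresholding is part of that protocol. A participant who feels unwell after thresholding and does not come back has no scheduled adverse-event record at all.

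**Working it through.** The protocol states no figure on this point, so there is none to reproduce. The check sets the sections side by side and then gives a scale.

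**Order of events (nominal days, sections 2 and 6.1.1 to 6.1.3)**

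| Visit | Day | Relevant procedures | Adverse-event tick |
|---|---|---|---|
| Screening visit 1 | 0 | Consent, randomisation, 7T scan | No |
| Screening visit 2 | 7 | Motor thresholding with single-pulse TMS | No |
| Visit 1 | 14 | First TMS or sham session | Yes |

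**Visits with real stimulation.** Each participant has one active and one sham session (5.6), and the sham coil's fields do not penetrate the skull (7.1.5). Someone who completes the study therefore receives real pulses at two visits: Screening visit 2 and the active session. One of these two has no scheduled record. For participants allocated to sham first, thresholding is the only real stimulation before the second session.

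**Length of the gap.**
- Consent to Visit 1: 14 − 0 = 14 days nominally.
- Screening visit 2 to Visit 1: 14 − 7 = 7 days nominally.
- Screening visit 2 to Visit 1 at the extremes of the ±7-day windows: (14 + 7) − (7 − 7) = 21 days.

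**Scale.** Inputs are n = 20 (synopsis) and p, the chance that a participant has an event linked to thresholding. The protocol gives no p for single-pulse TMS. Section 8.1 gives up to 10% for headache or neck pain with TMS in general; 1% and 5% are assumptions that show the range. The expected number of participants with an event is 20p, and the chance of at least one is 1 − (1 − p)^20.

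| p | Source | Expected, 20p | Chance of at least one |
|---|---|---|---|
| 1% | Assumed | 0.2 | 1 − 0.99^20 = 0.18 |
| 5% | Assumed | 1.0 | 1 − 0.95^20 = 0.64 |
| 10% | Section 8.1, upper rate for TMS in general | 2.0 | 1 − 0.90^20 = 0.88 |

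These are chances that an event occurs, not that it goes unrecorded.

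**Other routes by which an event could be captured.**
- *Reports to the Chief Investigator (8.5).* These have no start visit, so a faint or seizure at thresholding is within scope. The route depends on someone volunteering or noticing the event. Onward submission to the ethics committee is limited to related and unexpected events, whereas headache, neck pain, syncope and seizure are all listed as known effects in 8.1.
- *Withdrawal details on the eCRF (5.7).* These apply at any time and would document a drop-out, possibly with its cause. They do not cover participants who have an event and continue.
- *Looking back at Visit 1.* This is possible, but the protocol does not say it is done. It cannot help for someone who has withdrawn consent, because 5.7 then ends data collection.
- *Symptom diary, Days 8 to 14 (6.1.2).* It starts the day after the nominal thresholding visit. Its items are not described, and it is not identified as an adverse-event record.

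**The case against.** The strongest reply is that little would be lost in practice. Section 8.5 already brings these events to the Chief Investigator, 5.7 documents withdrawals, and adverse-event recording at Visit 2, two weeks after Visit 1, makes little sense unless it looks back. The same reading would let Visit 1 pick up the screening period. Thresholding uses single pulses and is done in everyone whatever their sequence. The safety summary in 9.2 is descriptive and limited to serious events, so a headache would not appear in it even if recorded. All of this stands, and it keeps the point small. It does not remove the mismatch, because none of these routes is a scheduled record and looking back is nowhere stated.

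A reader might infer more than the protocol supports:

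- *That drop-out caused by thresholding is lost.* Section 5.7 names adverse events as a reason for withdrawal and requires the details on the eCRF without limit to particular visits.
- *That events before Visit 1 would necessarily go unrecorded.* Reporting under 8.5 and looking back at Visit 1 both remain possible.
- *That the visit lists confirm the gap because 6.1.1 and 6.1.2 have no adverse-event item.* Sections 6.1.3 to 6.1.6 have none either, although those four visits are ticked in the schedule. The lists prove nothing either way.
- *That there is no baseline for headache or neck pain before the first session.* The diary covers Days 8 to 14 and its items are not shown, so this cannot be asserted.
- *That thresholding is the heavier exposure because it needs pulses at threshold while the session uses 90% of it.* The session delivers 1200 pulses in 10 Hz trains, so intensity alone is not a fair comparison.

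**Conclusion.** The inconsistency is real. The schedule begins adverse-event recording at Visit 1, while section 8 covers procedures that consented and randomised participants undergo up to 14 nominal days earlier, including their first real TMS pulses. No record is scheduled at one of the two visits with real stimulation, and a participant who stops before Visit 1 reaches no scheduled record. Sections 8.5 and 5.7 close the gap only in part.

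The number of events affected is unknown. The 18% rests on an assumed 1% rate. The 88% applies a general upper rate for TMS to single pulses, and to treat it as the chance of a missed event would further assume that no other route captures anything. It is an upper bound, not an estimate. The finding does not depend on either figure.

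The active-versus-sham contrast is not affected. This is a worthwhile correction to safety recording at almost no cost, not a threat to the trial's results.

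**What to change.** 1. In the section 2 schedule, tick "Recording of Adverse Events" at Screening visits 1 and 2.
2. State in 8.5 that recording runs from consent, so that the schedule and section 8 agree.
3. In 9.2, count serious events between consent and Visit 1 as a separate pre-session period. They then enter the overall summary without being attributed to either session.
4. If the item is also added to the section 6.1 visit lists, add it to all six visits. Adding it to the two screening visits alone would create a new mismatch.

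The cost is two ticks, a sentence each in 8.5 and 9.2, the existing eCRF form opened at two more visits, and a few minutes per screening visit. Non-serious events would be on record but would still lie outside the 9.2 summary, which this change leaves limited to serious events.

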3 INTRODUCTION

3.1 BACKGROUND

Rheumatoid arthritis (RA) is a common disease which is characterised by severe joint inflammation and chronic pain¹. The discovery of new joint specific treatments has transformed patient outcomes and yet most patients, even those whose joints respond fully to these treatments, continue to experience significant levels of pain^{2,3}. We therefore believe that RA pain is caused by alternative sources in addition to the joints.

Our group are pioneering the investigation of a possible link between the brain and the pain which RA patients experience. By employing sophisticated brain scanning methods, we have shown that high levels of pain and blood inflammation are associated with changes within a specific region of the brain known as the left inferior parietal lobule (L-IPL)⁴. This region exhibited abnormal connections with other brain regions already known to be associated with pain in another chronic pain disorder called fibromyalgia. Fibromyalgia is a musculoskeletal condition which is not classically related to high levels of blood inflammation, although, interestingly, it is not uncommon for it to co-exist in RA patients^{5,6}. In light of our preliminary brain scan studies, we now think that fibromyalgia in the context of RA may be partially influenced by inflammation.

In order to fully understand the precise processes that lead to this potential relationship, it is important to characterise the biological abnormalities that underlie our brain scan observations. Previous animal experiments have consistently observed abnormalities, such as high levels of the brain chemical glutamate and haphazard brain activity, in the context of inflammation. Conducting similar experiments in humans is not practical due to the inherent dangers of sampling live brain tissue. Instead, neuroscientists commonly use non-invasive methods to manipulate specific parts of the brain in order to better understand how they function. In conjunction, the latest scanners are now able to indirectly measure the effect of the brain modulation on relevant aspects of brain biology without the need to remove tissue⁷. This information will help us to better understand the relationship between inflammation and pain in the RA brain.

3.2 RATIONALE

Rheumatoid Arthritis-related pain is only partially explained by joint specific inflammation. Despite excellent control of peripheral inflammation by contemporary immune modulatory regimes, as many as 50% of patients continue to report disabling levels of pain, thus comprising an urgent unmet clinical need^{2,3}.

We have been among the first to evidence a contributory role of the central nervous system (CNS) as an explanation for this apparent disconnect^{4,8}. Our cross-sectional neuroimaging studies have implicated the left inferior parietal lobule of the brain as a critical interface between inflammation and pain. Not only did this region associate with levels of patient reported pain and indicators of systemic inflammation, but it was found to be functionally hyperconnected to brain networks established to be nociceptive in CNS based chronic pain disorders such as fibromyalgia. In parallel, preclinical experiments suggest that systemic inflammation leads to heightened glutamate neurotransmission, which in turn results in disorganised neuronal signal activity and ultimately altered functional connectivity between regions of the brain. In RA patients, we hypothesise that systemic inflammation-related neural glutamate enhancement triggers chaotic neuronal signalling, followed by compensatory hyperconnectivity with pro-nociceptive functional brain networks. Thereby, we believe that dysfunctional inflammatory processes in RA not only mediate nociception in vulnerable joints but also nociception in vulnerable regions of the brain.

Given the clear practical constraints of sampling fresh human brain tissue, we propose to test our hypothesis by combining state-of-the-art non-invasive brain modulatory techniques alongside leading-edge neurobiological surrogate imaging measures. Transcranial magnetic stimulation (TMS) is the neural modulatory probe of choice for neuroscientists seeking to infer causality of specific brain cortical regions^{9, 10}. Ultra-high resolution 7T MRI enables measurement of functional connectivity and haphazard neuronal signal activity at significantly superior spatial resolution compared to standard 3T approaches and can uniquely assess regional glutamate.

As a critical first step, this feasibility study aims to pilot a transcranial magnetic stimulation (TMS) protocol designed to target the L-IPL in RA. We will evaluate its effect employing ultra-high resolution 7T functional and glutamate measures. This novel project will inform a larger study which will aim to provide more robust evidence for the proposed neural pain interface between systemic inflammation and pain. Such knowledge could potentially support the analgesic testing of existing compounds e.g. alternative/augmented immunosuppressants or neural glutamate modulatory agents; and reverse translated in order to more precisely dissect the culprit mechanisms which in turn may inform the development of novel pain therapeutics. Both represent core aims of Versus Arthritis and address critical priorities among the patient populations that we serve.

